**Table 2: Effect of XPO1 Inhibition on Oncogenic and Inflammatory Pathways**

Pathway Affected	Effect of XPO1 Inhibition	Reference
XPO1 overexpression	XPO1 reduction	Walker 2013
Glucocorticoid Receptor (GR) Inactivation (nuclear export)	Nuclear GR retention (in presence of glucocorticoids) and reactivation	Chen 2014
p53 mutation	p73 activation, p21 activation	Ranganathan 2012
hDM2 (MDM2) activation	Nuclear p53 retention and activation, hDM2 protein reduction	Kojima 2013
c-Myc amplification	MYC protein reduction	Schmidt 2013
Cyclin D1 overexpression	Cyclin D1 reduction	Gao 2014
NPM1 mutation	Restoration of nuclear NPM1	Falini 2007
CEBPA down-regulation	Nuclear retention and activation	Ranganathan 2012
CDKN2A reduction	p53/p73 stabilization	Azmi 2013
Rb reduction	Rb hypophosphorylation, p14/p16 elevation	Fragomeni 2013
FLT3 activation	FLT3 reduction	Ranganathan 2012
c-KIT activation	c-KIT reduction	Ranganathan 2012
NF-κB activation	IkB nuclear retention and activation	Lapalombella 2012
PIK3 or AKT activation	FOXO1, -3, -4 activation	Lapalombella 2012
Survivin – cytoplasmic	Survivin nuclear retention	Altura 2003
Bcr-Abl activation	PP2A activation	Walker 2013

## 4. SELINEXOR (KPT-330)

### 4.1. Introduction

Selinexor is an oral, first-in-class, slowly reversible, potent selective inhibitor of nuclear export (SINE) compound that specifically blocks exportin 1 (XPO1). XPO1 is responsible for the unidirectional export of ~220 different cargo proteins from the nucleus to the cytoplasm (*Xu et al., 2010*). The anti-neoplastic activity of SINE compounds is mediated

through at least three distinct pathways involving tumor suppressor proteins (TSPs), oncoproteins, and the glucocorticoid receptor. First, SINE compounds induce nuclear localization and functional activation of multiple TSPs, leading to rapid apoptosis of multiple myeloma (MM) (*Tai et al., 2014*) and other malignant cells. By forcing the nuclear localization and activation of TSPs, all cell types exposed to SINE compounds undergo G1 ± G2 cell cycle arrest, followed by a ‘genomic fidelity’ review. Cells with genomic damage (ie, malignant cells) are induced to undergo apoptosis both in vitro and in vivo. Normal cells, with an intact genome, remain in transient, reversible cell cycle arrest until the XPO1 block is relieved. A second anti-neoplastic effect of SINE compounds is mediated through the mRNA cap-binding protein eIF4E, which is also an XPO1 cargo. Amongst other functions, eIF4E is responsible for the efficient nuclear export and delivery of several growth-promoting (oncoprotein) mRNAs to cytoplasmic ribosomal for translation. By forcing the nuclear retention of the eIF43 bound to XPO1, SINE compounds reduce the cytoplasmic ribosomal synthesis of oncoprotein mRNAs including c-Myc, hDM2, Cyclin D1 and Bcl-XL. Finally, SINE compounds also lead to restoration of anti-myeloma glucocorticoid receptor (GR) signaling in the presence of glucocorticoids; selinexor and other SINE compounds do not appear to exacerbate the hyperglycemic effects of glucocorticoids. Thus, by inhibiting the key nuclear/cytoplasmic control protein XPO1, SINE compounds exhibit broad and deep anti-cancer activities.

## 4.2. Preclinical Data

In this section, a brief summary of preclinical data is provided. Additional information is presented in the current *Selinexor/KPT-330 Investigator’s Brochure*.

*In vitro* experiments with continuous (~72 hour) exposure to selinexor demonstrated potent pro-apoptotic activity across a broad panel of tumor-derived cell lines and patient samples in culture, including multidrug-resistant cancers. Moreover, selinexor demonstrated cytotoxicity in MM and CLL cells in the absence or presence of bone marrow stroma cells (BMSC).

Pharmacokinetic (PK) studies were conducted in mice, rats and monkeys. Selinexor showed dose proportional exposure with no accumulation. Please see the current *Selinexor/KPT-330 Investigator’s Brochure* for more information.

Several studies were conducted to evaluate the effect of SINE compounds on MM *in vivo*. In MM1.S xenograft tumors, treatment with the SINE compound KPT-276 showed a marked decreased in tumor volume (40%) whereas tumor volume increased by 36% with placebo (*Schmidt 2013*). KPT-276 was also active in the Vk\*MYC mouse model of MM, which has a positive predictive value of 67% for the activity of single-agent compounds in clinical trials (*Schmidt 2013; Chesi 2012*).

### 4.2.1. Selinexor plus Dexamethasone Combination Studies

*In vitro* studies showed selinexor and dexamethasone in combination were found to have a synergistic effect on reducing MM1.S human MM cell viability relative to either drug alone (*Chen 2014*). Increased GR nuclear localization and concomitantly activated GCR-mediated transcription in the presence of glucocorticoids were at least partly responsible for the synergistic cytotoxicity of this combination. (*Gao 2014*).

Enhanced activity of the selinexor plus dexamethasone combination was also observed in two xenograft models of human MM. The addition of dexamethasone to selinexor enhanced activity (86%) relative to selinexor alone.

In summary, the combination of selinexor and dexamethasone is synergistic *in vitro* and *in vivo* in MM cell cytotoxicity assays through increased nuclear localization of GCR and amplified GCR transcriptional activity. Taken together, these studies demonstrate that SINE compounds are active anti-MM compounds that cause decreased cell viability, increased apoptosis, and cell cycle arrest *in vitro* and potent inhibition of MM tumor growth *in vivo*, and that the addition of dexamethasone can augment these effects.

### **4.3. Clinical Experience**

As part of a Phase 1 clinical study of selinexor in patients with advanced hematological malignancies (KCP-330-001), 68 patients with MM that was relapsed and/or refractory to all available classes of approved therapies and was progressing on study entry received selinexor on a twice-weekly dose schedule. Preliminary results, as of 13 December 2016, are summarized below.

#### **4.3.1. Preliminary Results for Patients with MM, Study KCP-330-001, as of 13 December 2016**

##### **4.3.1.1. Preliminary Efficacy Results for Patients with MM, Study KCP-330-001**

###### **Selinexor plus Dexamethasone**

As of 13 December 2016, the best responses among the 22 evaluable patients who received selinexor plus dexamethasone (Sd) were: 1 CR (5%), 5 PRs (23%), 3 MRs (14%), 8 SDs (36%), and 5 PDs (23%). The ORR was 27% and the CBR was 41%. Several patients remained on study for >9 months and one patient remained on study for >1 year.

###### **Single-agent Selinexor**

Selinexor showed modest efficacy as a single-agent with 4% of patients achieving an objective response ( $\geq$ PR in 2 of 46 patients) and 26% showing clinical benefit ( $\geq$  MR in 12 of 46 patients). Overall, these preliminary Phase 1 results suggest that selinexor  $\pm$  dexamethasone has clear anti-MM activity in heavily pretreated patients.

##### **4.3.1.2. Preliminary Safety Results for Patients with MM, Study KCP-330-001**

Adverse events in patients receiving single-agent selinexor were generally low-grade, consistent with events observed in patients with other hematological malignancies and responsive to standard supportive care. Preliminary Results for Patients with MM, Study KCP-330-012, as of 01 December 2016

Preliminary efficacy and safety results from the first 79 patients were presented at the 2016 American Society of Hematology annual meeting and are summarized below ([Vogl et al., 2016](#)).

#### 4.3.1.3. Preliminary Efficacy (Response) Results for Patients with MM, Study KCP-330-012

Response rates in patients with MM previously treated with lenalidomide, pomalidomide, bortezomib, carfilzomib, and refractory to one proteasome inhibitor (PI), one immunomodulatory drug (Imid) and glucocorticoids (“quad” refractory) and in patients with MM refractory to the “quad” agents as well as to an anti-CD38 Ab (“penta” refractory) were adjudicated by an Independent Review Committee (IRC) and are presented in Table 3. for the first portion of the study overall, for 8 vs. 6 doses per 28-day cycle and “penta” vs. “quad” MM (Vogl et al., 2016). One patient did not have measurable myeloma at baseline and is not included in the efficacy analyses. The ORR across all patients is 21% and the clinical benefit rate (CBR) is 33%. Similar ORR were seen in the patients with “penta” and “quad” MM, with higher CBR in patients who received 8 vs. 6 doses/cycle consistent with improved disease control with continuous dosing. The additional 122 patients with “penta” MM to be added will receive 8 doses / cycle based on these analyses.

**Table 3: Response by Doses per Cycle and Prior Therapy Status as of 01 Dec 2016**

Category	N a	ORR (%)	CBR (%)	VGPR (%)	PR (%)	MR (%)	SD (%)	PD (%)	NE (%)
Overall	78	16 (21%)	26 (33%)	4 (5%)	12 (15%)	10 (13%)	27 (35%)	9 (12%)	16 (21%)
8 doses/cycle	27	6 (22%)	11 (41%)	1 (4%)	5 (19%)	5 (19%)	6 (22%)	5 (19%)	5 (19%)
6 doses/cycle	51	10 (20%)	15 (29%)	3 (6%)	7 (14%)	5 (10%)	21 (41%)	4 (8%)	11 (22%)
Pentab	30	6 (20%)	12 (40%)	2 (7%)	4 (13%)	6 (20%)	6 (20%)	5 (17%)	7 (23%)
Quadc	48	10 (21%)	14 (29%)	2 (4%)	8 (17%)	4 (8%)	21 (44%)	4 (8%)	9 (19%)

CBR=Clinical Benefit Rate (sCR+PR+MR), MR=Minor Response, NE=Non-Evaluable, ORR=Overall Response Rate (sCR+PR), PD=Progressive Disease, PR=Partial Response, SD=Stable Disease, VGPR=Very Good Partial Response

a one patient not included, did not have measurable myeloma at baseline

b the majority of these patients (19 of 30) received 8 doses per cycle

c the majority of these patients (40 of 48) received 6 doses per cycle

#### 4.3.1.4. Preliminary Safety Results for Patients with MM, Study KCP-330-012

Common treatment-related adverse events (TRAEs) based on a preliminary analysis of safety and tolerability (N=92; safety data cut off 31 March 2017):

- Hematological: thrombocytopenia (overall: 64%, Grades 3/4: 51%), neutropenia (overall: 26%, Grades $\geq$  3 19%), and anemia (overall: 39%, Grade 3/4: 22%). There was one case of febrile neutropenia (1%) and one case of clinically significant bleeding related to thrombocytopenia (1%).

- Non-hematological: nausea (overall: 68%, Grade 3: 8%), fatigue (overall: 64%, Grade 3: 14%), anorexia (overall: 51%, Grade 3: 2%), vomiting (overall 41%, Grade 3: 2%), hyponatremia (overall 33%, Grade 3: 18%), diarrhea (overall 40%, Grade 3: 4%), and weight loss (overall: 33%, Grade 3: 1%).

These results are generally consistent with the overall TEAE results reported for all selinexor studies in patients with hematological malignancies (see the [Selinexor/KPT-330 IB](#)).

#### 4.3.1.5. Summary

Based on the promising preliminary efficacy results described above and on the considered feedback from MM experts that the population of patients with penta-refractory MM represents a current and growing high unmet medical need where there are no approved agents and there is no established standard of care, Karyopharm is expanding the number of patients with penta-refractory MM enrolled in this single-arm study to a total of ~160 patients with penta-refractory MM to receive Sd twice weekly for every week of each four-week cycle (8 doses/cycle).

#### 4.4.1. Reproductive Risks

Macroscopic and microscopic changes in reproductive organs were noted during rat and monkey toxicology studies; most resolved or partially resolved during the recovery period. The long-term effects of these changes on reproductive potential are unknown. Secondary developmental effects due to reduced maternal body weights were also noted during a study on rat embryo/fetal development. Please see the Selinexor (KPT-330) Investigator's Brochure for additional information. As it is unknown if selinexor produces any reproductive toxicity in humans, all patients must agree to use effective contraception (see Section 11.4.7) during the study and for 3 months after the end of treatment.

## 5. RATIONALE FOR THE STUDY

Multiple myeloma is the second most common hematological malignancy. With conventional treatment methods, median survival is 5.2 years after diagnosis (*Kumar 2014*). Multiple myeloma is highly treatable but is not considered to be curable with currently available therapies. Common treatments include glucocorticoids, chemotherapy, proteasome inhibitors, immunomodulatory drugs, stem cell transplants, and radiation therapy.

Selinexor has demonstrated anti-MM activity in pre-clinical studies *in vitro* and *in vivo*. A summary of clinical results for 81 patients with MM seen in Study KCP-330-001, as of 01 August 2016, is provided in Section 4.3.

The original design of this protocol (KCP-330-012) was based on the primary treatment options for RR MM (i.e., IMiDs and PIs) that were in common use at the time that the protocol was developed, in order to evaluate whether selinexor would provide a useful, new therapeutic option to patients whose disease was RR to these treatments (i.e., patients with quad-refractory MM). In that design, a subset of patients with penta-refractory MM was also included as an **CCI**, as treatment with anti-CD38 mAbs was not yet common. With the recent approval of daratumumab and ongoing development of isatuximab, the clinical use of anti-CD38 mAbs to treat RR MM has become more common, suggesting that selinexor would be best considered as a therapeutic option in patients with penta-refractory MM.

### 5.1. Rationale for Selinexor Dose Schedule

More than 2,000 patients with advanced cancers have received selinexor in Phase 1 and Phase 2 studies as of 31 March 2017. In study KCP-330-001, patients who received selinexor

45 mg/m^2 (~80 mg) plus dexamethasone 20 mg, both dosed twice weekly, experienced durable response without clinically relevant cumulative toxicities. (See Section 4.3.)

Patients in the present study will receive selinexor 80 mg (45 mg/m^2 BSA) plus dexamethasone 20 mg, both dosed twice weekly, for each week of four-week cycles.

Dexamethasone 20 mg will be given with each dose of selinexor. For patients with partial intolerance to glucocorticoids (as determined by the Investigator) a minimum dose of dexamethasone 10 mg with each dose of selinexor is permitted. If any patient is not able to tolerate this dose, then a potential discontinuation or further decrease in dosage would be allowed after a discussion with the Medical Monitor on a case by case basis.

In select cases (e.g., for patients showing SD or PR and tolerating treatment particularly well), the selinexor dose may be increased by 20 mg to 100 mg, based on efficacy and safety considerations, after a minimum of two cycles of study therapy. However, in no case may the dose for any patient exceed 70 mg/m^2. Prior to any potential dose increase, the BSA for the patient should be calculated. Patients with BSA < 1.4 m^2 may not have their dose increased, as this would result in a dose > 70 mg/m^2 selinexor.

## 6. STUDY OBJECTIVES

### 6.1. Primary Objectives

Evaluate the efficacy (overall response rate [ORR]) for treatment with selinexor 80 mg plus low-dose dexamethasone (20 mg) (Sd) twice weekly (four-week cycles) in patients with MM previously treated with lenalidomide, pomalidomide, bortezomib, carfilzomib, and daratumumab; and refractory to prior treatment with glucocorticoids, an immunomodulatory agent (IMiD), a proteasome inhibitor (PI), and the anti-CD38 mAb daratumumab (herein referred to as “penta-refractory” MM).

ORR will include patients who experience partial response (PR), very good partial response (VGPR), complete response (CR), or stringent complete response (sCR), based on International Myeloma Working Group (IMWG) response criteria (*Kumar 2016*) for patients with penta-refractory MM in Part 2 (expansion phase).

### 6.2. Secondary Objectives

The following endpoints will be analyzed separately for (a) Part 1 patients with quad-refractory MM, (b) Part 1 patients with penta-refractory MM, and (c) Part 2 (expansion) patients with penta-refractory MM. Additionally, analyses of safety and tolerability will be performed on the overall population of patients from Parts 1 and 2 who received at least one dose of study treatment.

- Duration of response (DOR = Duration from first observation of at least PR to time of disease progression, or death due to disease progression, whichever occurs first. DOR will be censored for death due to any causes other than disease progression)

- Lytic lesions as assessed by skeletal survey (or similar bone imaging)

## 7. STUDY DESIGN

### 7.1. Overview

This is a Phase 2b, single-arm, open-label, multicenter study of Sd (selinexor 80 mg plus dexamethasone 20 mg), both dosed twice weekly, four weeks of each four-week cycle, in patients with MM previously treated with lenalidomide, pomalidomide, bortezomib, carfilzomib, and daratumumab, and refractory to prior treatment with glucocorticoids, an immunomodulatory agent (IMiD), a proteasome inhibitor (PI), and the anti-CD38 mAb daratumumab. (Note: Refractory is defined as  $\leq 25\%$  response to therapy, progression during the previously described therapies, or progression within 60 days after completion of therapy.)

This study consists of two parts and will enroll approximately 210 patients overall. Part 1 (protocol V1.0-3.0) enrolled patients with both quad-refractory MM and penta-refractory MM. Part 2 (protocol V $\geq$ 4.0) will enroll patients with penta-refractory MM only, but continue all patients enrolled in Part 1.

The population for the primary efficacy analysis will contain only patients with penta-refractory MM enrolled in Part 2. Efficacy results for patients with quad-refractory MM and patients with penta-refractory MM enrolled in Part 1 will be analyzed separately. Safety analyses will be performed on the overall population of patients who received any amount of study treatment, presented overall and by study part, and separately for Part 1 penta-refractory MM patients and quad-refractory MM patients.

Patients will receive selinexor 80 mg (45 mg/m^2 BSA) plus dexamethasone 20 mg (Sd), both dosed twice weekly, for each week of four-week cycles. Patients will receive treatment until PD, death, toxicity that cannot be managed by standard care, or withdrawal, whichever occurs first.

Patients will also receive best supportive care to mitigate selinexor side effects, including blood product transfusions, antimicrobials, and (as appropriate) growth factors including granulocyte colony-stimulating factors for neutropenia, erythropoietins for anemia, and/or platelet-stimulating factors for thrombocytopenia.

In select cases (e.g., for patients showing SD or PR and tolerating treatment particularly well), the selinexor dose may be increased by 20 mg after consultation with the Medical Monitor. The dose level for an individual patient may be escalated based on efficacy considerations only after a minimum of 2 cycles of study therapy. However, in no case may the dose for any patient exceed 70 mg/m^2. Prior to any potential dose increase, the body surface area (BSA) for the patient will be calculated and an individual patient's dose may not be increased if it would result in a dose  $> 70$  mg/m^2.

In Part 2, MM-specific assessments (i.e., SPEP, UPEP, serum/urine immunofixation, quantitative Ig levels, serum FLC, and bone marrow aspirate) must be confirmed by a central laboratory to confirm CR or sCR, and select VGPR, per IMWG. Additional information is provided in the *Study Manual*.

The Investigator may remove a patient from study treatment using criteria described in Section 10.2. Patients may decide to discontinue study treatment for any reason. Patients who elect to discontinue study treatment should be encouraged to continue in the study so that follow-up information on disease progression, other antineoplastic therapy, symptoms and survival status may be obtained. However, patients may elect to withdraw consent and decline further participation in the trial at any time.

The Investigator must determine the primary reason for a patient's discontinuation of study treatment and record this information on the electronic case report form (eCRF). Patients who are prematurely withdrawn from study treatment are not eligible to re-initiate study treatment on this protocol at a later date.

## **7.2. Data Safety Monitoring Board**

An independent Data Safety Monitoring Board (DSMB) will review the safety of study treatment and any SAEs that occur during the study. Details on how the DSMB will review safety and response data are provided in the *DSMB Charter*.

The DSMB will be comprised of a minimum of two oncologists (at least one of whom specializes in hematologic oncology) and a statistician. Following their initial meeting, DSMB meetings will occur on a periodic basis in accordance with their charter.

## **7.3. Independent Review Committee**

An Independent Review Committee (IRC), will review disease assessment data to independently assess disease response. The IRC will review data that will be used for the analysis of the primary endpoint. The IRC's assessments of disease response and time to progression (TTP) will be used as the basis for the evaluation of the primary endpoint.

The IRC membership, functioning, and procedures (including resolution of any disagreements with Investigators regarding disease assessments) will be described in the *IRC Charter*.

## **7.4. Stopping Rules**

The entire study or treatment of individual patients may be stopped under defined circumstances as outlined in Section 10.

## **7.5. Study Endpoints**

Study objectives and endpoints are provided in Section 6.

## **7.6. Blinding and Randomization**

Not applicable; this is an open-label, single-arm, multicenter study.

## **7.7. End of Study**

The End of Study (EoS) will occur when all patients have completed the one-year Follow-up Period (i.e., when the last patient has expired, been followed for 12 months after last dose of study drug, been lost to follow-up, or has withdrawn consent, whichever occurs first).

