-  After treatment discontinuation, if possible, for patients who are not progressing, SPEP with serum immunofixation, UPEP (24 hr.) with urine protein immunofixation, serum FLC, and quantitative Ig levels (and physical examinations and imaging for bone lesions and plasmacytomas, if clinically appropriate) should be performed every 3 months for 1 year to assess durability of response. If these assessments cannot be performed, and for patients with PD, a telephone call will be made to the patient (or the patient's family) every 3 months for one year to inquire about the patient's survival, MM status, well-being, and information on any antineoplastic therapies utilized since discontinuation of selinexor study treatment.
-  Serious adverse events that occur after signing patient signs the ICF (including prior to first dose on C1D1) and adverse events that occur after first dose on C1D1.

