#### 11.1.5.5. Dose Escalation

In select cases (e.g., for patients showing stable disease or partial response and tolerating treatment particularly well), the selinexor dose may be increased by 20 mg after discussion with the Medical Monitor. However, in no case may the dose for any patient exceed 70 mg/m^2. Prior to any potential dose increase, the BSA for the patient should be calculated.

CCI

CCI Patients will be followed as long as possible or until disease progression and death.

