1.4. STUDY PLAN

For each patient that signs the informed consent, the study consists of:

- Screening/baseline visit: occurs within 21 days prior to receiving the 1st dose of study treatment
- Treatment period: expected to be up to 12 months, but there is no maximum treatment duration. Patients will be treated until disease progression, death, toxicity that cannot be managed by standard care, or withdrawal from study, whichever occurs first
- Follow-up period: up to 12 months after last dose of study treatment, patients will be contacted approximately every 3 months for durability of response and survival follow-up

The End of Study (EoS) will occur when all patients have completed the 12-month follow-up period (i.e., when the last patient has expired, been followed for 12 months after last dose of study treatment, been lost to follow-up, or has withdrawn consent, whichever occurs first).

Please refer to Table 7-1 for detailed schedule of assessment and study activities.

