4.2.7. Overall Survival (OS)

4.2.7.1. Definition

OS is defined as the duration from start of study treatment to death from any cause. If death event did not occur during the follow-up period, the patient is censored at the date of discontinuation from the study, or date of last participating visit (e.g., a telephone contact with patient status being alive), or database cut date, whichever is earlier.

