4.2.7.2. Analysis Methods

The proportion of patients with death event and the 2-sided, exact 95% CI will be calculated using the mITT population. Median OS time with 95% CI will be estimated based on the Kaplan-Meier method. The Kaplan-Meier curve for OS will be provided.

The following supportive OS analyses will be conducted:

- Using the BCLPD-ref, CLPD-ref, BCPD-ref, CPD-ref populations respectively
- Using the all penta-ref, high-risk, EE, PP, Part 1 – Quad, Part 1 – Penta, respectively, if sufficient data exist

- The same as in primary OS analysis except additional censoring at the start date of a new MM treatment
- In patients with R-ISS for MM stage I, II, and III respectively, if sufficient data exist
- In US vs. non-US patients, if sufficient data exist
- In FLC MM vs. non-FLC MM patients, if sufficient data exist
- In patients with a best response of confirmed PR or better
- In patients with a best response of confirmed MR or better
- In patients with a best response of confirmed MR
- In patients with a best response of SD or worse (including patients whose disease is not evaluable)

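### Survival follow-up stops 12 months after each patient's own last dose while OS runs from first dose, so Kaplan-Meier OS beyond month 12 is open to informative censoring, probably upwards

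*Protocol*

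**What the plan says.** - **Origin and estimator.** SAP 4.2.7.1: "OS is defined as the duration from start of study treatment to death from any cause". SAP 4.2.7.2: "Median OS time with 95% CI will be estimated based on the Kaplan-Meier method". Protocol 13.3.4 also asks for the 25th and 75th percentiles.
- **Patient-level limit.** SAP 1.4: "Follow-up period: up to 12 months after last dose of study treatment, patients will be contacted approximately every 3 months". Protocol Table 1, footnote 15, has telephone contact "every 3 months for one year to inquire about" survival and disease status. That footnote expressly covers patients who have progressed.
- **Study-level end.** Protocol 7.7 keeps the study open until the last patient has died, has "been followed for 12 months after last dose of study drug", is lost or has withdrawn consent.
- **Censoring.** SAP 4.2.7.1: "If death event did not occur during the follow-up period, the patient is censored at the date of discontinuation from the study", or at the last participating visit or the data cut, if earlier.
- **Sensitivity analysis.** The only alternative OS censoring rule in SAP 4.2.7.2 adds censoring at the start of new myeloma therapy.
- **A stray sentence.** Protocol 11.1.5.5 (Dose Escalation) has, directly after a redaction: "Patients will be followed as long as possible or until disease progression and death".

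**The concern.** Kaplan-Meier treats patients censored at a given time as having the same outlook as those who stay under observation. Here the plan decides who is censored when, by how long they stayed on drug. A patient who stops at month 1 is followed to about month 13; one who stops at month 12 is followed to about month 24. Under the protocol's treatment rule (synopsis, Methodology) drug stops for progression, toxicity that cannot be managed, withdrawal or death, so early stoppers probably do worse. As they leave, the later curve describes the long-treated patients while being reported for everyone.

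At stake are the OS curve after month 12, any percentile that falls there, and the many OS breakdowns in SAP 4.2.7.2, including those by best response. The effect belongs mainly to the final analysis. At the primary analysis, after the Cycle 2 assessments (SAP 1.6), censoring by calendar date matters more, especially for recent enrollees. Nothing forces the early cut-off: enrolment is planned over about 24 months and the study stays open until the last patient finishes, so early-enrolled patients who stop early can leave observation while the trial is still running.

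**Working it through.** The plan states no OS rate, median or OS event target, so there is no figure of its own to reproduce. The check has a structural step, which follows from the documents, and a size step, which needs assumptions.

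**Structure.** Let D be time from first to last dose and R survival after last dose, in months. For a patient who stops drug alive:
- survival time T = D + R
- planned censoring time C = D + 12

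Both contain D. At time t beyond 12, patients off drug are still under observation only if D > t − 12:
- t = 18: last dose after month 6
- t = 24: last dose after month 12, although SAP 1.4 expects treatment to last up to 12 months

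Since D cannot be negative, C cannot be below 12. The rule therefore censors nobody before about month 12, and Kaplan-Meier to that point is untouched.

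**Size.** All inputs here are assumptions:
- D exponential, median 2 or 4 months; 10% die on drug
- R exponential, median 4, 7 or 12 months, multiplied by (D / median D)^g, where g > 0 means that longer treatment goes with longer later survival
- optionally, gamma heterogeneity in R with variance 0.5 or 1

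With 400,000 simulated patients per scenario, Kaplan-Meier minus true survival, in percentage points, was:

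| Assumption | Month 18 | Month 24 |
|---|---|---|
| Link (g = 0.25 or 0.5), no heterogeneity | +0.7 to +3.3 | +1.3 to +6.9 |
| Link plus heterogeneity (R median 7) | −0.1 to +1.5 | −1.2 to +2.7 |
| No link, constant hazard after stopping | +0.1 to +0.8 | +0.1 to +1.8 |
| OS exponential, independent of stopping | about 0 | about 0 |
| No link, heterogeneous survival after stopping | −0.1 to −1.6 | −0.6 to −3.8 |
| Reverse link (g = −0.25, R median 7) | −1.3 to −3.5 | −1.9 to −6.9 |

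At month 12 the difference was zero in every row.

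Worked case (median D 2, median R 7, g = 0.5, no heterogeneity):
- month 12: 35.2% true, 35.2% by Kaplan-Meier
- month 18: 22.1% true, 24.4% by Kaplan-Meier, error 24.4 − 22.1 = +2.3
- month 24: 14.4% true, 19.0% by Kaplan-Meier, error 19.0 − 14.4 = +4.6

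The Kaplan-Meier median was unaffected when the true median was below 12 months, and otherwise moved by at most about 0.5 month.

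**Second model.** Two prognostic classes were also tried. The assumptions were that 25–40% of patients benefit (protocol Table 3 gives a Part 1 penta-refractory CBR of 12/30 = 40%), that median time on drug is 5–6 months in them and 1.5–2 in the rest, and that median survival is 15–24 against 6–10 months. 24-month OS was overstated by 2.3 to 5.5 points, and the 75th percentile by about 0.4 to 7.2 months. This model builds in the favourable link, so it shows size given that link and is not evidence for the direction.

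**The case against.** **Direction.** A reader might infer that the OS tail is necessarily biased upwards. The documents do not support that. An early stopper is censored by this rule only after surviving a year off drug, so those censored are selected survivors. If survival after stopping varies widely between patients and is unrelated to time on drug, the error turns negative, as the table shows. The documents give no OS or time-on-treatment data to settle it. Upwards is the more likely direction because treatment runs to progression, but no more can be said.

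**Practical weight.** OS is a descriptive secondary endpoint without a comparator. The only planned efficacy test is ORR against 10%, and the protocol's Amendment 1 history records that OS would not be tested. With 122 patients under the two-class model, the 24-month standard error was 5.2 to 6.3 points (95% CI about ±10 to ±12), with some 2 to 7 patients at risk, against an error of 3.0 to 4.2 points. The error is thus smaller than one standard error, in a visibly sparse tail. This stands and limits the importance of the point. It does not remove it, because the cause is a planned rule that can be changed cheaply.

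**TTNT.** A reader might extend the point to time to next treatment. That is not shown: next therapy or death usually follows soon after stopping, so few patients may reach the 12-month limit, and no size has been established.

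**Protocol 11.1.5.5.** A reader might call its open-ended sentence a contradiction of the one-year limit. It follows redacted text in the dose-escalation section, so its subject may be hidden, and no contradiction can be established.

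**Conclusion.** The concern holds in a limited form. That planned censoring after month 12 depends on time on drug follows directly from the protocol and SAP, and no planned analysis addresses it. OS estimates beyond 12 months at the final analysis are therefore subject to informative censoring, probably upwards. Under the assumed inputs the error at 24 months is roughly +1 to +7 points if longer treatment goes with longer survival and survival after stopping is not otherwise heterogeneous. It is near zero or negative if there is no link and survival after stopping is heterogeneous. Those figures depend wholly on assumed treatment and survival times. OS to 12 months, a median below 12 months and the primary ORR test are unaffected. This is a worthwhile improvement to a secondary endpoint and does not threaten the trial's main conclusion.

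**What to change.** 1. Keep the 12-month limit for disease assessments. In protocol Table 1 footnote 15, protocol 7.7 and SAP 1.4, add that survival status of every living, consenting patient is recorded to one common date, the final data cut.
2. In SAP 4.2.7.1, censor patients known to be alive at that date there, and count deaths up to it. Patients who are lost or withdraw consent stay censored at last contact.
3. If follow-up is not extended, show numbers at risk, caveat OS after month 12, and add a sensitivity analysis with inverse-probability-of-censoring weights based on time of and reason for stopping. Declaring all later quantiles not estimable would go too far: it would suppress, for example, a median of 13 months that is barely affected.
4. Check the sentence in protocol 11.1.5.5 against the one-year limit.

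The cost of items 1 and 2 is some further survival contacts, of a kind already planned, while the study is open. Item 3 is SAP wording and programming. Item 4 is editorial.
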